Our group has established effective tobacco interventions that demonstrate increased quit attempts and smoking cessation from: 1) gain-framed messaging, and 2) nicotine replacement therapy (NRT) sampling. Based on the tenets of Prospect Theory and an accumulating body of evidence from our previous studies, messages emphasizing the benefits of smoking cessation (i.e., gain-framed) are more effective than messages emphasizing the risks of continued smoking (i.e., loss-framed) for increasing intentions to quit, quit attempts, and smoking cessation in general populations of smokers. Our work also includes several studies showing that sampling of cessation medications leads smokers (both motivated and not) to increased cessation. Together, gain framed messaging and NRT sampling offer a novel and compelling opportunity to engage smokers and catalyze cessation. Our methods, if shown to be successful, can be easily shared with lung cancer screening programs across the country. Thus, we plan to conduct a randomized trial of gain-framed intervention (yes vs. no) x NRT sampling (2-week supply of both nicotine patch and lozenge vs. not) within a high-risk group of smokers (N=367) across 3 study sites (MUSC, VA and Yale). This study is powered to examine main effects of our 2 interventions:

**Primary Aim 1:** *To determine if the rate of smoking cessation among lung screening patients is improved by delivering gain-framed smoking cessation messages and delivery of a free starter package of medication (gain-framed behavioral intervention + 2 weeks of nicotine patches and lozenges vs. unframed behavioral intervention + no medication).*

**Hypothesis 1:** Cessation rates will be significantly higher at 6-months after lung screening for the smoking cessation strategy involving a gain-framed intervention + 2 weeks of nicotine patches and lozenges compared to a strategy of an unframed behavioral intervention + no medication. We define cessation as 7-day point prevalence but will assess multiple definitions of success.

**Exploratory Aim:** *To examine mediators and moderators of treatment to determine mechanisms of treatment effects and which subgroups are most likely to respond to the gain-framed and medication interventions, and to explore differential effects of the study factors across treatment groups. Treatment interactions will also be explored secondarily.*

[figure not shown]

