Our proposed study will also evaluate important moderators of response to the intervention. Several framed message intervention studies from our group and other research groups have found that patient characteristics can moderate treatment efficacy (e.g., baseline characteristics such as tobacco dependence measured by the Fagerström scale, which may be very relevant in this patient population). We will evaluate nicotine dependence as a moderator of treatment outcomes, and anticipate that participants with lower nicotine dependence scores will have higher quit rates overall regardless of condition assignment but there will be a differential benefit of gain-framed messaging and medication for those with higher nicotine dependence scores. Further, very large disparities in tobacco use remain across groups defined by race, ethnicity, educational level, and socioeconomic status. These groups, plus those with mental illness who smoke, are at an increased risk for tobacco-related health disparities. Given the disparities in tobacco use and health among these groups, we will evaluate these variables and determine if they moderate treatment outcomes. We also anticipate that smoking outcomes may be affected by the lung screening findings. That is, perhaps a scan that identifies emphysema would motivate a patient to quit smoking. Because research is lacking on how screening findings affect the efficacy of personalized, gain-framed messaging and NRT sampling, we will carefully evaluate these factors and determine if lung screening findings moderate our intervention.

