### **Design and Methods:**

#### **General overview:**

We propose a group comparison study (gain-framed intervention vs. unframed intervention, starter package of 2 weeks of nicotine patches and lozenges vs. no medication) to evaluation methods to boost rates of smoking cessation for a high-risk group of smokers (N=367) with varying levels of motivation across 3 study sites (MUSC, Ralph H. Johnson Veteran Administration and Yale). All eligible study participants will be randomized to receive either: 1) Unframed Messaging (hereafter referred to as UM) with no medication, or 2) Gain-framed Messaging + Meds (i.e., 1 gain-framed video and print materials + 2 week starter pack of NRT; hereafter referred to as GM+M).

**Participants:** Our target sample will be 367 lung screening patients who currently smoke at each of 3 study sites: MUSC), Ralph Johnson VA, and Yale Cancer Center); Total N=367. The following eligibility criteria will ensure that we obtain our study sample of lung screening patients. **Inclusion:** 1) 50 years or older (we see no reason for an upper limit given supportive evidence for cessation among elderly), 2) at least a 20 pack year history of smoking (i.e., the base population of high risk smokers to get screened) as assessed by the patients ordering healthcare provider or the research team, 3) current smoker (defined as any smoking in the past 30 days – this is the criteria our lung cancer screening programs will use to trigger tobacco treatment interventions), 4) willing to be randomized, 5) English speaking; **Exclusion:** 1) unstable psychiatric/medical conditions such as suicidal ideation, acute psychosis, severe alcohol dependence, or dementia, and 2) known allergy to adhesives, and 3) current participation in another tobacco treatment program (e.g., using medication from a primary care doctor, quitline, etc).

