### **Statistical Considerations**

#### **Power and Sample size:**

We propose to test the primary hypothesis that rates of smoking cessation will be significantly higher 6-months after lung screening for the smoking cessation strategy involving a gain-framed intervention + 2 weeks of nicotine patches and lozenges compared to a strategy of an unframed behavioral intervention + no medication. We assume a biologically confirmed 7-day point prevalence abstinence rate at the 6 month follow up visit of 10-13% for the participants randomized to receive no NRT or gain framed messaging based on USPHS guidelines (Table 6.7 and 6.8 of USPHS Guidelines). In studies with a similar 2 week NRT exposure, 6 month abstinence rates varied from 16-34 % and a conservative estimate of a 20% abstinence rate in those receiving NRT only will be assumed. Based on previous work we estimate that the abstinence rate of in those receiving both NRT and gain framed messaging will be 10-11% increased over those with unframed messaging. Based on these estimates, we will have 80% power with a type 1 error rate of 5% to detect the conservative difference of between those receiving gain framed messaging + NRT (28%) and those receiving unframed messaging and no NRT (13%) with 123 participants randomized to each of the 4 treatment groups (total n=492 Participants). This assumes that the two treatment sites are moderately correlated (ICC=0.85) and randomize equal numbers of patients to each treatment cell. Additionally, we anticipate that 15-20% of our participants will fail to report 6 month follow up outcome data (LTF, death, moved out of area), accounting for a 20% attrition during the study follow up, we would need to randomize **n=367 participants** across all sites (179 randomized at Yale and 179 between MUSC and the VA) to maintain adequate power to detect the clinically meaningful difference stated. Assuming an abstinence rate of 14-17% in the group receiving unframed messages, we will have >80% power with a type 1 error rate of 5% to detect an 11% increase in abstinence in those receiving gain framed messages with the sample size stated for aim 1. We considered but opted against powering our trial on the treatment interaction, as this would require >5,000 participants.

Anticipated abstinence rates – 6 months	Gain-framed Intervention	No Message Intervention	
2 week starter pack NRT	28-30%	18-20%	23-25%

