*We have an exploratory aim in which we plan to examine moderators of treatment to determine which subgroups are most likely to respond to the gain-framed and medication interventions, and we will explore differential effects of the study factors across treatment groups.* Procedures from MacKinnon et al. will be used to test mediators. We hypothesize that changes in self-efficacy, smoking cessation outcome expectancy, familiarization with NRT, motivation, and autonomy will act as mechanisms for the smoking cessation effects (i.e., will act as mediators of treatment). Variables that predict the outcome variable (smoking cessation) differently between treatments will be considered to be moderators using the model outlined by Kraemer et al. In order to be considered a moderator, the variable must be present prior to randomization and must not be related to the independent variable. We hypothesize that lung screening findings (e.g., presence of a nodule, cancer, etc.), nicotine dependence, and health disparities will modify treatment response (i.e., will act as baseline moderators of treatment). Variables that predict the outcome variable but do not significantly interact with treatment condition (i.e., influence outcome regardless of treatment condition) will be classified as nonspecific pre-randomization predictors.

*Our other exploratory aim will examine additional treatment endpoints: patient reach, intervention fidelity, patient acceptance and engagement, cost, and the ease of delivery and feasibility.* We hypothesize that we will reach a majority of qualified patients who are current smokers, adherence to the critical elements of the intervention design and delivery methods will be successfully met, patient acceptance and engagement will be greater in the gain-framed messaging and NRT arms, the cost will be higher in the NRT arms, and both the gain-framed messages and dispensing of the 2-week starter pack of NRT will be easily delivered and feasible as part of the lung screening clinic work flow. Patient adherence, exposure to study content, acceptance/responsiveness to content and noted distinguishing factors will be assessed within the study and across study groups. Associations between treatment status and these exploratory endpoints will be assessed using general linear mixed models with data appropriate residual distribution assumptions (Gaussian, Poisson, etc.) and transformations where necessary.

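### The moderator rule reads a non-significant treatment interaction as evidence of no moderation, although 367 participants give low power for interactions as large as the planned treatment effect

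*Combined protocol and SAP*

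**What the plan says.** Statistical Analysis introduces the work as exploratory: "We have an exploratory aim in which we plan to examine moderators of treatment". It hypothesizes that lung screening findings, "nicotine dependence, and health disparities will modify treatment response (i.e., will act as baseline moderators of treatment"). It then gives a two-way classification. A variable that predicts outcome differently between treatments is a moderator. Those that are associated with abstinence and "do not significantly interact with treatment condition (i.e., influence outcome regardless of treatment condition) will be classified as nonspecific pre-randomization predictors".

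The Specific Aims state the purpose as learning "which subgroups are most likely to respond to the gain-framed and medication interventions". The Significance section makes a specific forecast for dependence. Less dependent smokers are expected to quit more in either condition, and "there will be a differential benefit of gain-framed messaging and medication for those with higher nicotine dependence scores".

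For these interaction tests the plan gives no power, no minimum interaction size, no interval or equivalence criterion, no undetermined category and no statement on the number of tests. Power and Sample size does say that powering on the treatment interaction would take more than 5,000 participants. That remark concerns gain-framing by NRT, not treatment by baseline characteristic.

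**The concern.** Failing to detect an interaction is not evidence that none exists, unless the test had a good chance of detecting one that matters. The rule has no middle category: once a variable predicts abstinence, the interaction p-value alone decides between moderator and acting equally in both arms.

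The variables most exposed are those expected both to predict quitting and to modify the effect, and the plan says this of nicotine dependence. A report that follows the rule could state that such a variable works the same way in both arms when the data are compatible with a large difference. That would mislead on the question the exploratory aim asks.

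**Working it through.** **Inputs from the documents.** N: "we would need to randomize n=367 participants across all sites" (Power and Sample size). Two arms (General overview). Planned abstinence of 28% against 13% and a 5% type 1 error (Power and Sample size). Missing outcomes count as non-abstinent (Statistical Analysis), so all 367 are analysed.

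**Assumptions not in the documents.** 1:1 allocation (183.5 per arm), two-sided tests, 13% control abstinence in both moderator subgroups, average treated rate 28%, binary moderator with prevalence 25% or 50%, and effects that differ by 10 or 15 points between subgroups. Fifteen points equals the whole planned effect (28 − 13).

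**The plan's own figure.** There is none for moderators. For the main comparison it states 123 per group for 80% power. The usual two-proportion formula for 13% against 28% gives 113 without and 126 with continuity correction, so 123 is reproduced within 3%.

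**Interaction power, worked case.** Prevalence 50%, effects 22.5 and 7.5 points, 183.5/2 = 91.75 per cell, cell rates 13%, 35.5%, 13% and 20.5%.

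- Risk difference: SE = √[Σ p(1−p)/n] = √[(0.1131 + 0.2290 + 0.1131 + 0.1630)/91.75] = √0.00674 = 0.082. z = 0.15/0.082 = 1.83. Power = Φ(1.83 − 1.96) ≈ 45%.
- Log odds: difference in log odds ratios = ln(0.355/0.645) − ln(0.205/0.795) = −0.597 + 1.355 = 0.758 (the control terms cancel). SE = √[Σ 1/(n p(1−p))] = √[(8.84 + 4.37 + 8.84 + 6.14)/91.75] = √0.307 = 0.554. z = 1.37. Power = Φ(1.37 − 1.96) ≈ 28%.

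| Prevalence | Effects (points) | SE, risk difference | Power, risk difference | Power, log odds |
|---|---|---|---|---|
| 50% | 22.5 vs 7.5 | 0.082 | 45% | 28% |
| 50% | 20 vs 10 | 0.082 | 23% | 15% |
| 25% | 26.25 vs 11.25 | 0.099 | 33% | 20% |
| 25% | 22.5 vs 12.5 | 0.098 | 17% | 12% |

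Simulation of these scenarios gives about 18-46% and 9-28%. The plan specifies logistic models for abstinence, so the log-odds column is closer to what would be run. For 80% power in the worked case on that scale, N = 367 × (1.96 + 0.842)² × 0.307/0.758² ≈ 1,540.

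**From power to wrong labels.** The nonspecific label needs two things: an association with outcome and a non-significant interaction. Both were simulated at 5%, with 40,000 runs per scenario.

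- 50%, 22.5 vs 7.5, risk-difference test: association found in 44% of runs, wrong label in 20%. Given an association, 20/44 ≈ 45% are mislabelled.
- 50%, 20 vs 10: association in 22%, wrong label in 14%. Given an association, 14/22 ≈ 64%.
- 25% prevalence, risk-difference test: wrong label in 13-20%.
- All four scenarios, log-odds test: wrong label in 17-32%.
- Given an association, all four scenarios: about 44-71% (risk difference) and 73-89% (log odds).

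**Interval width.** 1.96 × 0.082 = 0.16 and 1.96 × 0.099 = 0.19. The 95% interval for an interaction therefore extends about 16-19 points either side.

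**The case against.** A reader might infer that one minus power is the mislabelling rate, and so that most true moderators would be declared non-moderators. The text does not support this. A variable must also predict abstinence to receive the label, and many missed moderators would not, so they go unclassified. The overall rate in these scenarios is 13-32%.

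The dependence example is also weaker than it looks. Higher quitting among the less dependent and larger benefit among the more dependent partly cancel in the overall association. With assumed control rates of 16-18% against 8-10%, the wrong label occurred in 4-19% of runs. The dependence measures are scores, not halves of the sample: a ratio of odds ratios per standard deviation of 2.0 has 70% power, though 1.5 has 31%. Very large binary interactions (25-30 points at 50% prevalence) reach 64-80% on the log-odds scale. All of this stands and limits the size of the claim.

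The aim is labelled exploratory, and the authors disclose that a different interaction is unpowered. That excuses low power and lowers the priority. It does not justify a definite label drawn from a non-significant result, and the classification sentence carries no caution.

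A reader might also want a figure for the chance of a false moderator. The plan fixes no list of tests, and the candidates overlap (the Heaviness of Smoking Index consists of two Fagerström items), so a calculation that assumes independent tests would overstate it.

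**Conclusion.** The concern holds as a fault in the inference rule. Following the sentence as written would attach a conclusion of no moderation to results that cannot support one. Under the stated assumptions, power for 10- to 15-point interactions is about 18-46% (risk difference) or 9-28% (log odds). About 13-32% of true moderators would be wrongly labelled, rising to about 44-89% among those with an overall association. These figures depend on assumed prevalence, interaction size and control rates, and they improve for very large interactions or strong continuous moderators. The documents do not support inferring that the primary comparison is at risk: it does not use this rule. Priority is low.

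**What to change.** In the moderator paragraph of Statistical Analysis:

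1. Delete the bracketed inference that such variables act alike in both arms.
2. Report every treatment-by-moderator interaction as an estimate with its 95% confidence interval.
3. Label variables that predict outcome without a significant interaction *predictor of outcome; moderation not determined*.
4. State how many moderators were tested, so that significant ones are read as hypothesis-generating.

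An equivalence margin of, say, 10 points is not a workable alternative. An interval with a half-width of 16-19 points cannot fit inside it, so no binary moderator could meet it at this sample size. A false-discovery-rate adjustment need not be mandatory, since it would cost power that is already low.

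The cost is one revised sentence and one table, with no new data. The downside is fewer definite labels.

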**NRT sampling:** Participants in the medication arm (GM+M) will be given a 2-week long supply of both nicotine patch and lozenge. NRT samples will be delivered in addition to all standard care treatment described above. Given the very brief 'intervention' time (few minutes), we believe that treatment groups will be essentially time-matched. We will provide a 2-week supply of both 4 mg lozenge and 21mg nicotine patches provided in the original packaging. Detailed information on each product, including instructions for use, will be provided in the take-home packet, which will include FAQs and related information intended to dispel medication misperceptions. Patients who are receiving nicotine patches and lozenges will be given the option to try these over-the-counter products (i.e., a patch and a lozenge) at the time of their study visit with aid from the research staff and will receive handouts and instructions about proper use of the NRT. We provide both patch and lozenge for four reasons. **First**, a number of studies demonstrate their efficacy when used singularly. **Second**, they are both over the counter, increasing their utility in various populations, particularly within lung cancer screening settings where eligibility is minimal and instructions on use require nominal discussion. **Third**, whereas the patch provides a steady dose of nicotine throughout the day, the lozenge is used ad libitum and provides acute nicotine administration. These two mechanisms might appeal to smokers differently. **Fourth**, two studies have shown that combined use of patch + lozenge is superior over placebo and single NRT products. We neither explicitly advise nor discourage combined use. Thus, this is an opportunity for smokers to learn about two NRT products, to be used individually or together (participant choice, including none at all). We will caution all participants on signs of receiving too much nicotine (nausea, dizziness), and will monitor adverse events, expected to be rare/mild. Given our inclusive study criteria, some study participants who have low nicotine dependence will receive the starter package of NRT. However, given recent evidence that dual NRT benefits most low dependence smokers, we feel this is appropriate. We do not offer a placebo comparison because we are interested in the provision of medication vs. not (and not to determine if effects are pharmacologic). However, participants not receiving the starter kit of NRT will still be advised to use evidence based medications, including NRT, per standard guidelines. The NRT for MUSC patients will be stored in a cabinet in the Tobacco Treatment Program offices. The door to the office suite locks. The NRT for VA patients will be obtained via the research pharmacy at the Ralph H Johnson VA Medical Center.

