Adverse Events (AE) and Serious Adverse Events (SAE) will be recorded during the duration of the treatment period. All cause treatment emergent adverse event and serious adverse event frequencies will be compared through the use of analysis of variance models. Of particular interest will be (S)AEs that lead to treatment suspension or study discontinuation. Study retention will be assessed by two methods; total number of treatment visits attended will be compared using Poisson regression for count data, while the number of days retained will be assessed using Cox Proportional Hazards regression models.

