**Plan for grading adverse events.** Serious Adverse Events (SAE). The FDA's definition of serious adverse events (21 CFR 312) will be used. Serious Adverse Events include any untoward medical occurrence that at any dose results in death or the immediate risk of death, hospitalization or the prolonging of an existing hospitalization, persistent or significant disability/incapacity or a congenital anomaly/birth defect, new cancer, or medication overdose. Adverse events will be defined and graded for risk as follows:

Coding of Severity:

- 0 = No adverse event or within normal limits
- 1 = Mild adverse event
- 2 = Moderate adverse event
- 3 = Severe, resulting in psychiatric or medical hospitalization
- 4 = Life-threatening adverse event
- 5 = Fatal adverse event

Coding of Attribution will be made for adverse events grade 3 and above (ie, serious adverse events):

- 1 = Unrelated to study interventions
- 2 = Unlikely relationship to study interventions
- 3 = Possible relationship to study interventions
- 4 = Probable relationship to study interventions
- 5 = Definite relationship to study interventions

**Plans for reporting serious unanticipated and anticipated adverse events.** Serious adverse events, whether unanticipated or anticipated, will be reported immediately (within 24 hours) to the MUSC Institutional Review Board, the Yale University Human Investigation Committee, and to the National Cancer Institute, and a written report will be submitted within 48 hours. The PI will evaluate the adverse event and determine whether the adverse event affects the Risk/Benefit ratio of the study and whether modifications to the protocol or the consent procedures are required.

**Plans for reviewing and reporting nonserious anticipated or unanticipated adverse events.** Any participants' experiences of anticipated and unanticipated adverse events will be reported on an annual basis to the MUSC Institutional Review Board, the Yale University Human Investigation Committee, and the National Cancer Institute as part of an annual progress report (NCI) and annual re-approval (MUSC Institutional Review Board and the Yale University Human Investigation Committee).

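### Adverse event and SAE frequencies are to be compared by analysis of variance, whose interval for a risk difference is too narrow when events are few and then tends to understate excess harm

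*Combined protocol and SAP*

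**What the plan says.** The last paragraph of Statistical Analysis covers safety. It states that AEs and "Serious Adverse Events (SAE) will be recorded during the duration of the treatment period", and that all-cause treatment-emergent AE and "serious adverse event frequencies will be compared through the use of analysis of variance models". No other test is named for them, and no interval is specified. The text does not say whether a frequency is the number of participants with an event or the number of events. It singles out events that led to treatment being suspended or to leaving the study.

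The NRT sampling text under Study Interventions says that staff "will monitor adverse events, expected to be rare/mild", without giving a rate. The Data and Safety Monitoring Plan defines SAEs to include hospitalisation and also "new cancer, or medication overdose".

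For similar data the plan chooses differently: chi-square for categorical baseline variables, logistic regression for abstinence, and Poisson regression for the number of visits attended, the last in the same paragraph as the ANOVA sentence. The exploratory endpoints get mixed models with a residual distribution suited to the data, but that sentence does not extend to adverse events.

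**The concern.** ANOVA assumes roughly normal errors with equal variance in the arms. A yes/no outcome has variance p(1 − p), so the variances differ whenever the risks differ, and with few events the distribution is far from normal. An interval from the model is symmetric about the observed difference and shrinks towards zero width as the counts approach zero. For a safety comparison that is the unhelpful direction: an arm with no or few events would seem to rule out an excess that the data cannot rule out. At stake is how the safety table is read, above all for SAEs and for events that ended participation, which are a subset of all events and so sparser.

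**Working it through.** **Inputs.** The overview gives a "high-risk group of smokers (N=367) with varying levels of motivation across 3 study sites" and two arms ("All eligible study participants will be randomized to receive either: 1) Unframed Messaging"). The sample size text assumes that sites "randomize equal numbers of patients to each treatment cell". I therefore take 184 in the NRT arm and 183 in the control arm. The 5% level is stated for efficacy ("80% power with a type 1 error rate of 5"%); I assume two-sided 5% here. The documents give no AE rate, AE power or AE sample size, so there is no planned figure to reproduce, and all event rates below are assumptions.

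**Formulas.** With a events among n1 and b among n2, let p1 = a/n1, p2 = b/n2 and d = p1 − p2.

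- ANOVA: s² = [n1·p1(1 − p1) + n2·p2(1 − p2)]/(n1 + n2 − 2); SE = s·√(1/n1 + 1/n2); F = (d/SE)²; interval d ± t·SE, with t = 1.966 on 365 df.
- Newcombe (score-type): with Wilson limits (l, u) for each arm, lower = d − √[(p1 − l1)² + (u2 − p2)²] and upper = d + √[(u1 − p1)² + (p2 − l2)²].

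**Example, 1 v 0 events.** p1 = 1/184 = 0.543%. s² = 184 × 0.005435 × 0.994565/365 = 0.002725. SE = √[0.002725 × (1/184 + 1/183)] = 0.545 points. The ANOVA interval is 0.543 ± 1.966 × 0.545, or −0.53 to 1.62 points. The Wilson limits are 0.10% to 3.01% for 1/184 and 0 to 2.06% for 0/183, so Newcombe gives −1.56 to 3.01 points. With 0 v 0 the ANOVA interval has zero width, while Newcombe runs about 2 points either side of zero.

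**P-values.** For 4 v 0, ANOVA gives 0.0451 and uncorrected chi-square 0.0449; for 7 v 1 both give 0.0326. Enumerating all outcomes of two binomial arms with a common rate gives these type I error rates at nominal 5%:

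| Event rate | 0.25% | 0.5% | 1% | 2% | 5% | 10% |
|---|---|---|---|---|---|---|
| ANOVA | 0.2% | 1.1% | 3.8% | 4.5% | 4.9% | 5.0% |

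Fisher's exact test gives 0.9% at a 1% rate and 2.5% at a 2% rate.

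**Intervals.** The same enumeration with different rates gives the percentage of trials in which the 95% interval misses the true excess (nominal 2.5% each side):

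| True rates, NRT v control | ANOVA wholly below | ANOVA wholly above | Newcombe wholly below |
|---|---|---|---|
| 3% v 0.5% | 6.18 | 1.11 | 1.27 |
| 2% v 0.5% | 4.60 | 0.55 | 0.70 |
| 1% v 0.1% | 15.74 | 0.23 | 0.01 |
| 10% v 5% | 2.85 | 2.09 | 2.45 |

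The third row can be checked by hand. With no event in the NRT arm the ANOVA upper limit is at most 0.53 points, below the true excess of 0.9, and the chance of no event is 0.99^184 = 0.157. Putting 183 in the NRT arm instead changes the first column only slightly (for example 4.7% at 2% v 0.5%).

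**Event counts.** In simulations with 10,000 runs per setting, ANOVA's type I error was 3.4% to 5.3%. A plain Poisson comparison reached 17% under assumed overdispersion (negative binomial, k = 0.3, mean 0.3 events).

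**The case against.** The strongest reply is that the choice does little damage. A reader might infer that ANOVA gives wrong p-values here; the calculations do not support that. Overall type I error never exceeded 5% at the rates tried and was closer to nominal than Fisher's. Some splits do disagree with Fisher's test, but the disagreement is fragile. With the events in the arm of 184, Fisher gives 0.061 for 5 v 0 and 0.067 for 7 v 1; with them in the arm of 183 it gives 0.030 and 0.037, on the same side of 0.05 as ANOVA. Only 4 v 0 differs either way (Fisher 0.123 or 0.061). Conditional on exactly 4 events in total, ANOVA's false-positive rate is 12.3%, but that is the worst total from 1 to 12: it is 0% at 1 to 3 events, 3.0% at 6 and 2.0% at 10.

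Three further points stand in part. The plan promises a comparison and names no interval, so the interval fault arises only if one is taken from the ANOVA model. The expectation of rare, mild events comes from the NRT text, whereas the comparison covers all-cause events; hospitalisations and new cancers in smokers aged 50 or over with 20 pack-years need not be rare, and at commoner rates the fault largely goes. And NRT exposure is not confined to one arm, since controls are also advised to use evidence-based medication, including NRT.

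None of this makes ANOVA suitable for sparse yes/no data, or explains why the plan departs here from its own practice.

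**Conclusion.** The point holds, and it is minor. ANOVA is the only named method for AE and SAE frequencies, it does not suit such data, and it is out of step with the rest of the plan. The practical fault is an interval that is too narrow when events are few and misses mainly on the side that understates harm: wholly below the true excess in 6.2%, 4.6% and 15.7% of trials at 3% v 0.5%, 2% v 0.5% and 1% v 0.1%, falling to about 2.9% at 10% v 5%. These figures rest on assumed event rates, a 184 v 183 split, and counting participants with at least one event. Inflated overall type I error is not part of the finding. The point matters most for SAEs and for events leading to treatment suspension or withdrawal. No decision rule depends on the comparison, and safety oversight runs through event grading, expedited reporting and semiannual review.

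**What to change.** Replace the ANOVA sentence in the SAP. State the unit of analysis as the participant. By arm, give the number and percentage with at least one AE, at least one SAE, and at least one AE or SAE leading to study discontinuation, each with the risk difference and a score-type 95% interval such as Newcombe's. Report events leading to stopping study NRT descriptively in the NRT arm only, because the control arm is given no study NRT and there is nothing to compare with. If event counts are also analysed, use negative binomial regression with follow-up time (the time over which events were recorded) as offset, rather than plain Poisson.

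An exact test is optional. If one is added, say that it is conservative: size about 0.9% at a 1% rate, and at 3% v 0.5% with 184 in the NRT arm it detects the excess in 27% of trials against 46% for ANOVA. The cost is SAP wording and slightly wider intervals; no data collection or sample size changes.
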